7.0 TREATMENT PLAN

- 7.1 For treatment or dose modification related questions, please contact [name] (MedCon may also be used to contact MDs at [contact]).
- 7.2 Administration of therapeutic agents: Each cycle of therapy is given every 21 days. Pembrolizumab is given on day 1 at a fixed dose of 200 mg IV per standard of care. Cycle start date may be +/-3 days from the prior cycle. Infusion details should be as per institutional standard of care.

All subjects will start umbralisib at 800 mg daily and this will be given continuously throughout the cycle on days 1-21 (see 7.2.1 for more information). Pembrolizumab will be continued for a total of 16 cycles on this study,

regardless of the number of cycles of previous treatment with pembrolizumab before entering the study. Patients may discontinue pembrolizumab early based on criteria listed in 7.4.5. Umbralisib will be continued indefinitely until disease progression or unacceptable toxicity. The order of administration is not specified in this trial. Further recommendations are listed in section 8.

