7.4 Criteria for removal from protocol treatment

7.4.1 Documented progression of disease by Lugano criteria (see appendix 3)¹⁴. Since anti-PD1 agents can be associated with tumor flare and mixed responses that may meet Lugano criteria for progression¹⁵, subjects may continue treatment on protocol

beyond progression at the discretion of the investigator provided that the subject is clinically benefiting from the treatment. Examples of clinical benefit include but are not limited to overall decrease in tumor burden and improvement in symptoms.

7.4.2 If at any time the constraints of this protocol are detrimental to the subject's health and/or the subject no longer wishes to continue protocol therapy, protocol therapy shall be discontinued, the principal investigator shall be notified, and the reason for discontinuation shall be documented.

7.4.3 Delay of treatment for more than 8 weeks for either pembrolizumab or umbralisib due to related adverse events unless prophylactic measures can be taken for subsequent cycles. Treatment delays of greater than 8 weeks are permitted at investigator discretion and with notification of TG Therapeutics. If only one agent is discontinued, the other agent should be continued provided that at least one of the following criteria is met.

- The subject has received at least 6 cycles of therapy.
- Achieved a FDG-PET-defined CR

7.4.4 The subject may withdraw from the treatment at any time for any reason.

7.4.5 Subjects may opt to discontinue pembrolizumab prior to completing 16 cycles of treatment and continue receiving umbralisib if they have one of following

- Achieved a FDG-PET-defined CR
- Received a minimum of 6 additional doses of pembrolizumab after achieving a PR.

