- Immune-mediated Pneumonitis – discontinue for Grade 3-4 or recurrent Grade 1-2 pneumonitis

- Colitis – Grade 4
- Immune-mediated Hepatitis – Grade 4
- Immune-mediated Endocrinopathies – (excluding endocrinopathies controlled with hormone replacement therapy)
 - Hyperthyroidism – Grade 4
- Immune-mediated Nephritis – Grade 3-4
- Infusion-related reaction – Grade 3 or 4
- Inability to reduce corticosteroid dose to 10mg or less of prednisone or equivalent per day within 6 weeks
- Persistent Grade 2 or 3 adverse reactions (excluding endocrinopathies controlled with hormone replacement therapy) that do not recover to Grade 0-1 within 4 weeks after last dose of pembrolizumab
- Any Grade 3-4 treatment-related adverse reaction that recurs
- Please refer to the FDA approved pembrolizumab prescribing information for more information.
- For treatment or dose modification related questions, please contact [name] (MedCon may also be used to contact MDs at [contact]).

8.2 Umbralisib dose reduction steps: If a subject undergoes a dose reduction, it should not be subsequently increased, even if the toxicity resolves to Grade 0. However, if further evaluation of the toxicity reveals the event was not related to umbralisib, this should be recorded in the medical record and dose re-escalation to the previous dose may be considered at the discretion of the investigator.

Drug	Starting Dose	1 st Dose Reduction	2 nd Dose Reduction
Umbralisib	800mg daily	600mg daily	400mg daily

Supportive care should be considered for any subject who experiences Grade \geq 2 cytopenias, or Grade \geq 1 non-hematologic toxicities.

NCI-CTCAE Grade	Umbralisib Dose Delay or modification
Hematologic Adverse Event	
Neutropenia	
Grade \leq 2 neutropenia	Maintain current umbralisib dose. Consider supportive care as warranted.
Grade 3 neutropenia	Maintain current umbralisib dose for first occurrence, consider supportive care. If recurrence or persistent Grade 3 after re-challenge, resume umbralisib at next lower dose level at discretion of the principal investigator/sub-investigator.
Grade 4 neutropenia or occurrence of neutropenic fever/infection	Delay umbralisib until Grade \leq 3 and/or neutropenic fever or infection is resolved; thereafter, resume at current dose. Consider supportive care. If recurrence after re-challenge, resume umbralisib at next lower dose level at discretion of the principal investigator/sub-investigator.
Thrombocytopenia	

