Grade \leq 3 thrombocytopenia	Maintain current umbralisib dose level and provide supportive care as clinically warranted.
Grade 4 thrombocytopenia	Delay umbralisib until Grade \leq 3; thereafter, resume at current dose. Consider supportive care intervention as warranted. If recurrence after re-challenge, resume umbralisib at next lower dose level at discretion of the principal investigator/sub-investigator.
Hepatitis	
Grade 2-3 AST/ALT or total bilirubin increase	Delay umbralisib until resolution to Grade \leq 1. If the subject has baseline liver involvement and grade 2 abnormalities at baseline, treatment may continue unless it worsens to grade 3. For grade 3 toxicity, reduce the umbralisib dose to the next lower dose level upon resolution to Grade \leq 1.
Grade 4 AST/ALT or total bilirubin increase	Permanently discontinue umbralisib.
Immune related pneumonitis*	
Grade 1-2	Stop all therapy (umbralisib and pembrolizumab) and hold until complete resolution. Restart umbralisib at one lower dose level. Restart pembrolizumab at current dose. If recurrence after re-challenge, discontinue all treatment therapy.
Grade \geq 3	Discontinue all therapy (umbralisib and pembrolizumab).

* For sinopulmonary infections clearly not related to immune-mediated pneumonitis, umbralisib may be continued at investigator's discretion. While pneumonitis has been minimal with umbralisib, it is a reported adverse event associated with other PI3K delta inhibitors. *Pneumocystis jiroveci* pneumonia (PCP) and anti-herpetic viral prophylaxis must be instituted as outlined in 7.2.1.

Diarrhea and/or colitis	
Diarrhea grade \leq 2	Maintain current umbralisib dose level if tolerable or hold and then resume at current dose level once has resolved. NOTE: If persistent grade 2 diarrhea, despite supportive care, delay umbralisib until \leq grade 1. If recurrence after rechallenge, resume umbralisib at current dose or next lower dose level at discretion of the principal investigator/sub-investigator.
Diarrhea \geq 3	Withhold umbralisib until Grade \leq 1. Resume umbralisib at current dose or next lower dose level as per discretion of principal investigator/sub-investigator. If recurrence after rechallenge, resume umbralisib at next lower dose level at discretion of the principal investigator/sub-investigator.
Colitis (all grades)	Hold umbralisib. Treat with supportive care and after resolution of colitis, resume umbralisib at next lower dose level
All other non-hematological events	

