9.0 STUDY CALENDAR

Required Studies	Screening	Cycle 1-4 Day 1	Cycle 1-4 Day 8	Restaging ⁵	Cycle 5-16 day 1	Within 3 days prior to every 4 th cycle starting with cycle 17 while on umbralisib alone	End of treatment ⁷	Follow-up ⁶
Scheduling window (days)	-42 to -1 ⁹	+/- 3 days	+/- 2 days		+/- 3 days			
Physical								
History and Physical	X	X ¹			X ³	X	X	
Performance Status	X	X ¹			X ³	X	X	
Clinical Disease Assessment	X	X ¹			X ³	X	X ⁷	X
Adverse Event Assessment	X	X ¹			X ³	X	X	
Concomitant Medication Assessment	X	X			X	X	X	
Lab²								
TSH, T3, T4, LDH, ESR ²	X			X		X	X	
CBC with differential	X	X ¹	X	X	X	X	X	
Comprehensive metabolic panel	X	X ¹	X	X	X	X	X	
Serum pregnancy test ⁴	X ⁴							
Hepatitis B/C serology, direct and indirect coombs, CMV	X							
CMV surveillance by PCR ¹⁰		X ¹⁰			X ¹⁰	X ¹⁰	X ¹⁰	
Radiology								
EKG	X							
PET/CT ⁵	X			X			X ⁷	
CT ⁵				X				
Correlative Studies ⁸	X	X		X	X			

1. For Cycle 1 Day 1, pre-entry H&P, performance status, disease assessment and adverse event assessment may be used (these do not need to be repeated within 3 days) and labs done within 14 days of cycle 1 day 1 are acceptable.
2. LDH and ESR must be done within 14 days prior to study entry.
3. Between cycles 6-16 history, physical, performance status, and AE assessment by the investigator/sub-investigator may be performed every 2 cycles at investigator discretion.
4. Serum pregnancy test in women of childbearing potential should be performed with screening and repeated within 3 days of cycle 1 day 1.
5. FDG-PET-CT should be performed at baseline within 42 days prior to first dose of cycle 1. Diagnostic quality CT is not required at baseline for subjects who have CT measurable lesions from CT component of FDG-PET-CT. Follow up CT-scans should be performed after day 1 of cycle 3, 6, 9, 12 and 16, but prior to day 1 of the next cycle. PET-CT should be performed on the next imaging assessment for: 1) subjects meeting CR criteria by CT, 2) subjects meeting criteria for PR on 2 consecutive images, 3) subjects being removed from protocol for reasons other than progressive disease (including end of treatment), and 4) at the discretion of the investigator. For patients continuing on umbralisib for cycle 17 and beyond, imaging should be performed at the discretion of the investigator and upon clinical suspicion of progression/relapse.

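### For some early toxicity stops of pembrolizumab, Sections 7.4.3 and 8.2 give opposing instructions on whether umbralisib continues, and the CR analysis does not say how such subjects are read

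*Combined protocol and SAP*

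**What the plan says.** Four parts of the protocol bear on a subject who permanently loses pembrolizumab to toxicity early in treatment.

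- **Section 7.2** sets the duration of umbralisib: "Umbralisib will be continued indefinitely until disease progression or unacceptable toxicity".
- **Section 7.4.3**, under the criteria for removal from protocol treatment, opens with "Delay of treatment for more than 8 weeks for either pembrolizumab or umbralisib due to related adverse events". It then adds: "If only one agent is discontinued, the other agent should be continued provided that at least one of the following criteria is met". The two criteria are "The subject has received at least 6 cycles of therapy" and "Achieved a FDG-PET-defined CR".
- **Section 8.1.2** lists the events that end pembrolizumab permanently. They include Grade 4 colitis, Grade 3-4 immune-mediated nephritis, and "Infusion-related reaction – Grade 3 or 4". None is tied to a cycle number.
- **Section 8.2** (umbralisib modification table) covers colitis of every grade in one row: umbralisib is held, then "Treat with supportive care and after resolution of colitis, resume umbralisib at next lower dose level". The row for other non-hematological events of Grade 3 or higher withholds umbralisib until Grade 1 or lower and provides for rechallenge. Neither row mentions 6 cycles or a CR.

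Section 7.4.5 adds a different condition for subjects who choose to stop pembrolizumab before 16 cycles and stay on umbralisib: a PET-defined CR, or at least 6 further pembrolizumab doses after a PR.

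Section 1.1 defines the primary objective as the CR proportion with the two-drug regimen. Sections 10 and 11 do not say how a CR first reached on umbralisib alone is counted.

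**The concern.** A site treating a subject with, for example, Grade 4 colitis in cycle 3 and no PET CR finds one section telling it to resume umbralisib and another that makes continuation depend on criteria the subject has not met. Two sites, or two investigators at one site, could follow the protocol faithfully and do opposite things.

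This matters in two ways. The subject is either removed or kept on a single agent. And the primary endpoint may be touched: a subject kept on umbralisib can still reach a CR, which might then be credited to the combination, while a removed subject is unlikely to be given that chance on study. In an open single-arm trial of 20 subjects, the choice would be made case by case by people who know how the subject is doing.

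**Working it through.** **1. The passages side by side, for a subject before 6 cycles and without a PET CR**

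| Event | Pembrolizumab (8.1.2) | Umbralisib (8.2) | Remaining agent (7.4.3) | Conflict? |
|---|---|---|---|---|
| Colitis, Grade 4 | permanent stop | hold, then resume after resolution | condition not met | yes |
| Nephritis, Grade 3-4 | permanent stop | withhold to Grade 1 or lower, rechallenge foreseen | condition not met | yes |
| Infusion reaction, Grade 3-4 | permanent stop | same row as nephritis | condition not met | yes |
| AST/ALT or bilirubin, Grade 4 | permanent stop (as hepatitis) | permanent stop | not applicable | no |
| Pneumonitis, Grade 3 or higher, or recurrent | permanent stop | all therapy stopped | not applicable | no |
| Progression | stop | ends under 7.2 | not applicable | no |

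The colitis row is the clearest case, because 8.2 states resumption outright. For nephritis and infusion reaction, resumption is implied by withholding to a recovery grade and by the reference to rechallenge.

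**2. Can the PET criterion settle it early?** Section 9.0, footnote 5, schedules CT in cycles 3 and 6. After a CT CR, PET comes one assessment later: "PET-CT should be performed on the next imaging assessment for: 1) subjects meeting CR criteria by CT". With 21-day cycles, cycle 3 is days 43-63 and cycle 6 is days 106-126. A PET before cycle 6 can be done at the investigator's discretion, or because the subject is being removed for a reason other than progression (the third trigger in footnote 5). Footnote 7 also strongly recommends end-of-treatment imaging. So the criterion can be tested at the time of the stop, but it resolves the conflict only for a subject already in CR.

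**3. The plan's own figure.** Inputs from Section 11.1: N = 20, null 16%, alternative 40%, one-sided level 0.1, stated power 88%. Exact binomial:

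- P(X ≥ 5 | 0.16) = 0.206, above 0.1.
- P(X ≥ 6 | 0.16) = 0.087, so the test rejects at 6 or more CRs.
- P(X ≥ 6 | 0.40) = 0.874, in line with the stated 88%.

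**4. Size per subject.** 1/20 = 5 points. This is the most that one affected subject can move the CR rate, and it needs a CR on umbralisib alone. The test turns on one CR (5 against 6), so a single subject could decide it, but only if the count is at that edge.

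**5. Illustration, not an estimate.** Assume k subjects are affected, the other 20 − k have a 40% CR rate, and the 6-of-20 rule is kept. If affected subjects are removed they count as non-CR. If they stay on umbralisib they reach CR with assumed probability q. Power = P[Bin(20 − k, 0.40) + Bin(k, q) ≥ 6].

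| k (assumed) | removed (q = 0) | kept (q = 5% to 20%) |
|---|---|---|
| 1 | 83.7% | 84.2% to 85.6% |
| 2 | 79.1% | 80.3% to 83.5% |
| 3 | 73.6% | 75.6% to 81.2% |

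The difference between the two readings is 0.5 to 1.9 points at k = 1 and 2.0 to 7.6 points at k = 3. The value q = 20% borrows the overall response rate that Section 2.0 reports for single-agent idelalisib. That is a different drug, the rate includes partial responses, and it makes no allowance for a lingering pembrolizumab effect. At q = 20%, the expected shift in the CR rate is k × 0.20/20, or 1 to 3 points for k = 1 to 3.

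**The case against.** **An ordinary reading may remove the conflict.** Section 7.2 is a general duration rule and a specific removal criterion can qualify it. Section 8.2 sets holds and dose levels for everyone, including subjects whose pembrolizumab is merely paused. The sentence in 7.4.3 follows a rule on delays over 8 weeks and may be confined to it. It also says the agent continues provided a criterion is met, without the word only. Part of this stands: the clash with 7.2 alone is weak. But 8.2 is as specific as 7.4.3, the 7.4.3 sentence speaks of an agent being discontinued rather than delayed, and its two criteria would do nothing if continuation were allowed without them. Each limiting reading is possible; no text adopts one.

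**Umbralisib alone is already part of the design.** Section 7.4.5 allows it after an elective stop, including in PR, and 7.2 allows it after cycle 16. This stands. A later CR on one drug can occur whatever is done about 7.4.3, so any separate reporting must distinguish toxicity stops from elective ones.

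**Stronger readings that the documents do not support.**

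- A reader might infer that every early pembrolizumab stop is affected. It is not: umbralisib stops too in the last three rows of the first table.
- A reader might infer from the imaging schedule that only a discretionary PET could show an early CR. Footnote 5 also calls for PET when a subject is being removed for reasons other than progression.
- A reader might take the 2 of the first 5 subjects in Section 7.5 as the rate of exposure. Those events were Grade 3 rash and Grade 3 ALT elevation, which on first occurrence are withhold events under 8.1.1. Section 7.5 does not say that either subject lost pembrolizumab permanently.
- A reader might multiply 5 points by a guessed number of subjects. That would require each of them to reach CR on umbralisib alone.

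**Conclusion.** The contradiction is real but narrow. For Grade 4 colitis, and through the row for other non-hematological events for Grade 3-4 nephritis or infusion reaction, a subject with fewer than 6 cycles and no PET-defined CR receives opposing instructions from 8.2 and 7.4.3, with nothing to say which prevails. This rests on reading the 7.4.3 sentence as reaching a permanent stop, which its wording permits but its position in the section leaves arguable.

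The number of subjects concerned cannot be derived from the documents. The effect on the primary result is bounded at 5 points per affected subject and is zero for any who would not reach CR on umbralisib alone. No figure in Section 11.1 is shown to be wrong. The point still deserves correction, because it decides whether a subject stays on treatment and leaves open what the two-drug CR rate contains.

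**What to change.** Reconcile Sections 7.2, 7.4.3, 7.4.5, 8.1.2 and 8.2 so that one rule applies when pembrolizumab is permanently stopped for toxicity before 6 cycles and before a PET-defined CR. State whether the 7.4.3 sentence is limited to delays over 8 weeks, and cross-refer to the rule from the colitis row and the row for other non-hematological events in 8.2. Which rule applies is a clinical decision for the sponsor; this review takes no view on it.

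In Section 11.1, state that these subjects stay in the denominator. Beside the primary CR rate, report the number of CRs first reached after one agent was permanently stopped, with toxicity stops shown separately from elective stops under 7.4.5.

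The cost is a wording amendment and one extra line from response and treatment data that the trial already collects. The drawback is that the line will describe a very small subset, so it should be given as counts without inference.

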7.5 Study stopping rules for immune-related toxicity

There is the potential for increased immune-related adverse events with combination of umbralisib and pembrolizumab. The study will be suspended and an ad hoc safety committee will be convened with individuals with appropriate expertise (majority of whom are not directly affiliated with the study) for consideration of results and appropriate modification or termination of the study if there is

sufficient evidence that the probability of Grade 3 or 4 immune-related adverse events that do not resolve to Grade ≤ 2 within 72 hours exceeds 20%. This will be deemed to occur if the lower level of a one-sided 80% confidence interval for this proportion exceeds 20%.

The protocol was originally written to determine if there was sufficient evidence that the probability of grade 3-4 immune-related adverse events exceeded 10%. This was based on earlier data, though follow up data from a study that combined umbralisib with pembrolizumab and a CD20 monoclonal antibody found 4/20 (20%) subjects had grade 3-4 transaminitis. This protocol hit the suspension rule when 2 out of the first 5 subjects met this (grade 3 rash and grade 3 ALT elevation).

An ad hoc safety committee was convened. Since there are no standard therapies beyond PD1 inhibitors in the treatment of classical Hodgkin lymphoma, it was felt that a higher threshold for toxicity was warranted. Therefore, the threshold was increased to suspend again if the lower level of a one-sided 80% confidence interval for this proportion exceeds 20% (increased from 10%)

In addition, a change was recommended to allow for prednisone treatment that exceeds 10 mg for 6 weeks before requiring discontinuation of the protocol.

There are 15 subjects remaining in the study to be enrolled. The study operation rules will include the first two subjects as meeting this criteria, and will mandate another suspension in the following circumstances

- If 4 out of the first 11 or fewer patients, or 5 out of the first 15 or fewer, or 6 out of 20 or fewer patients experience Grade 3 or 4 immune-related adverse events that do not resolve to Grade ≤ 2 within 72 hours.

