8.0 DOSAGE MODIFICATION, DELAY, OR DISCONTINUATION

8.1 Dose modification of pembrolizumab

8.1.1 Withholding pembrolizumab: Adverse events (both non-serious and serious) associated with pembrolizumab exposure may represent an immunologic etiology. These adverse events may occur shortly after the first dose or several months after the last dose of treatment (see below). The use of corticosteroids should be considered for management of immune-related adverse events (irAEs). Please refer to prescriber

manual for further detail on dosing of corticosteroids for pembrolizumab-related toxicity. If the drug-related toxicity does not resolve to Grade 0-1 within 4 weeks after onset of toxicity, discontinuation is recommended. Pembrolizumab must be withheld for drug-related toxicities and severe or life-threatening AEs as per the below criteria (may resume upon recovery to grade 0 or 1 toxicity unless otherwise noted below).

- Hematological toxicity- Grade 4; Pembrolizumab should be held until resolved to Grade ≤ 3 .
- Colitis, any Grade- Grade 2-3; also administer high-dose systemic corticosteroids (followed by a taper).
- Hyperthyroidism- Grade 3; administer high-dose systemic corticosteroids (followed by a taper).
- Hypophysitis- Grade 2-4; administer high-dose systemic corticosteroids (followed by a taper).
- Nephritis- Grade 2; consider administration high-dose systemic corticosteroids (followed by a taper).
- Pneumonitis- Grade 1-2; administer high-dose systemic corticosteroids (followed by a taper). Pembrolizumab may be resumed after resolution.
- Hepatitis- Grade 2-3. Pembrolizumab should be held until resolution to Grade ≤ 1 . If the subject has baseline liver involvement and Grade 2 abnormalities at baseline, treatment may continue unless it worsens to Grade 3.
- Other treatment-related toxicity, severe or Grade 3; may require high-dose systemic corticosteroids (based on severity). Upon improvement to grade 0 or 1, initiate corticosteroid taper and continue to taper over at least 1 month. Restart pembrolizumab if the adverse reaction remains at grade 0 or 1 and steroid dose is ≤ 10 mg. Please refer to the FDA approved pembrolizumab prescribing information for more information.

8.1.2 Discontinuing Pembrolizumab: If any of the following criteria are met, pembrolizumab should be permanently discontinued

- Confirmed radiographic disease progression per the appropriate tumor evaluation criteria.

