12.0 STUDY MONITORING AND REPORTING PROCEDURES

12.1 Adverse Event Reporting

Reporting of AEs and SAEs should commence after first administration of either umbralisib or pembrolizumab, and should continue for up to 30 days after

last dose of study treatment (pembrolizumab or umbralisib, whichever is given last).

Complete and timely reporting of adverse events (AEs) is required to ensure the safety of subjects. Reporting requirements are determined by the characteristics of the adverse event including the *grade* (severity), the *relationship to the study therapy* (attribution), and the *prior experience* (expectedness) of the adverse event. The guidelines outlined in this section, as well as the specific direction on each report form must be followed. The NCI Common Terminology Criteria for Adverse Events v5.0 (CTCAE) will be used to classify and grade toxicities. The CTC can be found on the Cancer Therapy Evaluation Program (CTEP) homepage at https://ctep.cancer.gov/protocolDevelopment/electronic_applications/docs/CTC_AE_v5_Quick_Reference_8.5x11.pdf

12.2 Definitions and descriptions of terms used in adverse event reporting.

Adverse Event (AE)

An *adverse event (AE)* is defined as any unfavorable and unintended sign (including an abnormal laboratory finding), symptom, or disease temporally associated with the use of a medical treatment or procedure. The investigator should log AEs that are deemed to be clinically significant and assess their attribution to either or both of the study medications.

Serious Adverse Event or Adverse Drug Reaction

A *Serious Adverse Event (SAE)* or *Adverse Drug Reaction (ADR)* means any AE/ADR occurring at any dose that results in:

- Death;
- A life-threatening AE/ADR (i.e, the patient/subject was, in the view of the initial reporter/investigator, at immediate risk of death from the AE as it occurred. It does not refer to an AE that hypothetically might have caused death if more severe);
- Inpatient hospitalization or prolongation of existing hospitalization (i.e, hospitalization was required to treat or diagnose the AE/ADR: excludes hospitalization for unrelated reasons);
- A persistent or significant disability or incapacity (disability here means that there is a substantial disruption of a person's ability to conduct normal life functions);
- A congenital anomaly/birth defect;

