- An important medical event (i.e., AEs/ADRs that might not be immediately life-threatening, or result in death or hospitalization might be considered serious when, based upon appropriate medical and scientific judgment, they might jeopardize the patient/subject or might require medical or surgical intervention to prevent one of the other serious outcomes listed above);

- Any suspected transmission via a medicinal product of an infectious agent.

Grade

Grade is defined as the severity of the adverse event. The CTCAE Version 5.0 must be used to determine the grade of the adverse event. If toxicity is not listed in the CTCAE use the following general criteria for grading.

- 0 – No adverse event or within normal limits
- 1 – Mild adverse event
- 2 – Moderate adverse event
- 3 – Severe adverse event
- 4 – Life-threatening or disabling adverse event
- 5 – Fatal adverse event

Attribution

Attribution is defined as the determination of whether an adverse event is related to a medical treatment or procedure. The investigator or authorized sub-investigator will assess attribution according to the following categories:

- *Unrelated*: the adverse event is *clearly NOT related* to therapy
- *Unlikely*: the adverse event is *doubtfully related* to therapy
- *Possible*: the adverse event *may be related* to therapy
- *Probable*: the adverse event is *likely related* to therapy
- *Definite*: the adverse event is *clearly related* to therapy

Unexpected Adverse Event

An *unexpected adverse event* is any adverse event that is not listed in the current Investigator's Brochure, package insert, protocol, or associated documents; or the specificity or severity of which is not consistent with these documents.

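### The Section 7.5 suspension count is worded as Grade 3 or 4 only, so read literally an immune-related event first graded as fatal (Grade 5) is not counted (minor)

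*Combined protocol and SAP*

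**What the plan says.** Section 7.5 states the monitored event twice. The probability statement concerns "the probability of Grade 3 or 4 immune-related adverse events" that have not come down to Grade 2 or lower within 72 hours, and asks whether that probability exceeds 20%. The listed counts require suspension when 4 of the first 11 or fewer, 5 of the first 15 or fewer, or 6 of 20 or fewer "patients experience Grade 3 or 4 immune-related adverse events that do not resolve to Grade" 2 or lower in that time. The criterion behind the counts is: "This will be deemed to occur if the lower level of a one-sided 80% confidence interval for this proportion exceeds 20" percent. Two of the first five subjects, both with Grade 3 events, are carried forward into the count.

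Section 12.2 grades severity from 0 to 5. Grade 4 is life-threatening or disabling; Grade 5 is separate and is defined as "Fatal adverse event".

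Nothing in 7.5 or elsewhere adds Grade 5 events to the count, and no separate numerical trigger for treatment-related death appears in the documents.

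**The concern.** A toxicity suspension rule should respond at least as readily to a death as to a Grade 3 rash. As worded, the grade range stops at 4. If the first or only grade recorded for an immune-related event is 5, a literal reader would leave it out, and another reader would include it as obviously meant. The choice would then be made after the event is known, with few events separating continuation from suspension: from 2 of 5, the rule needs 2 more by subject 11, 3 more by subject 15, or 4 more by subject 20.

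The gap is limited to that situation. An event recorded at Grade 3 or 4 and still unresolved at 72 hours has already been counted, whatever happens to the patient later.

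**Working it through.** **Inputs.** From Section 7.5: threshold 20%, one-sided 80% lower limit, boundaries 4/11, 5/15 and 6/20, and a starting position of 2 events in 5 subjects. From Section 11.1: 20 subjects. The proportion of qualifying events first graded as fatal is not in the documents, so 1% and 2% are assumptions.

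**Step 1: reproduce the plan's boundaries.** The exact (Clopper-Pearson) one-sided 80% lower limit for x events in n subjects is the 0.20 quantile of a Beta(x, n − x + 1) distribution.

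| Events/subjects | Lower limit | Above 20%? |
|---|---|---|
| 4/11 | 21.67% | yes |
| 4/12 | 19.79% | no |
| 5/15 | 21.32% | yes |
| 5/16 | 19.94% | no |
| 6/20 | 20.13% | yes |

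The three listed boundaries are reproduced: 11 and 15 are the largest sample sizes at which 4 and 5 events meet the criterion, and 6 events still meet it at 20.

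**Step 2: leave one event out at each boundary.**

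| Subjects | One event uncounted | All events counted |
|---|---|---|
| 11 | 3 events, 14.3%: continue | 4 events, 21.7%: suspend |
| 15 | 4 events, 15.7%: continue | 5 events, 21.3%: suspend |
| 20 | 5 events, 15.8%: continue | 6 events, 20.1%: suspend |

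One uncounted event reverses the decision at every boundary.

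**Step 3: expected effect.** Start at 2 events in 5 subjects and add subjects 6 to 20 one at a time, suspending when the count reaches 4 (n ≤ 11), 5 (n ≤ 15) or 6 (n ≤ 20). The probability that a subject adds a counted event is the true rate × (1 − share uncounted). The chance of suspension by subject 20 is:

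| True rate | None uncounted | 1% uncounted | 2% uncounted |
|---|---|---|---|
| 20% | 49.2% | 48.5% | 47.8% |
| 30% | 78.9% | 78.2% | 77.5% |
| 40% | 94.0% | 93.6% | 93.2% |

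The loss is about 0.4 to 0.7 points at 1%, and about 0.7 to 1.4 points at 2%.

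**Step 4: how often would such an event occur?** The chance of at least one among the 15 subjects still to enrol is 1 − (1 − true rate × share)^15.

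| True rate | 1% share | 2% share |
|---|---|---|
| 20% | 1 − 0.998^15 = 3.0% | 1 − 0.996^15 = 5.8% |
| 30% | 1 − 0.997^15 = 4.4% | 1 − 0.994^15 = 8.6% |
| 40% | 1 − 0.996^15 = 5.8% | 1 − 0.992^15 = 11.4% |

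**Limit of these figures.** They use the listed counts. The stated criterion is also met at 3/6 (26.86%) and 3/7 (22.83%), which the list omits. Applying the criterion itself, with nothing uncounted, gives 58.2%, 83.1% and 95.3% at true rates of 20%, 30% and 40%. That mismatch is a separate matter.

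**The case against.** The strongest reply is that this is drafting shorthand. The protocol uses closed and open grade ranges loosely. For pneumonitis, Section 8.1.2 says "discontinue for Grade 3-4 or recurrent Grade 1-2 pneumonitis", while the row of the Section 8.2 table labelled Grade ≥ 3 says "Discontinue all therapy (umbralisib and pembrolizumab"). Those rules concern discontinuing treatment, where Grade 5 has no practical meaning, so they are weak evidence on what 7.5 intends; if anything they favour the shorthand reading. The 72-hour clause also favours inclusion, since a fatal event does not improve to Grade 2. This stands, and it is why the point is minor. It does not settle the wording: the closed range appears in both operative statements of 7.5.

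A second reply is that a death would not go unnoticed. This also stands. Under 12.4, serious events go to the drug supplier within 24 hours, and unexpected fatal events associated with study drug go to the FDA within 7 days. Under 12.5, committees review at least annually and as needed, and their approval, as applicable, is required for the study to continue. Section 7.5 says when suspension is mandatory; it does not bar earlier action. What these routes lack is a number that requires suspension.

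Two stronger readings are tempting. A reader might infer that the rule is substantially weakened. If one randomly chosen event among subjects 6 to 20 is removed from every outcome that has any, the chance of suspension falls from 49.2% to 28.0%, from 78.9% to 60.2%, and from 94.0% to 84.6% at true rates of 20%, 30% and 40%. But this presumes an uncounted death in nearly every trial (at least one event occurs in 96.5% or more of outcomes), whereas Step 4 puts the chance at about 3 to 11% under the 1 to 2% assumption.

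A reader might also infer that late immune-related events escape the rule, because 8.1.1 says "These adverse events may occur shortly after the first dose or several months after the last dose of treatment" while 12.1 ends reporting 30 days after the "last dose of study treatment (pembrolizumab or umbralisib, whichever is given last"). That some events may be late does not contradict a 30-day window. Umbralisib continues until progression or unacceptable toxicity, which keeps the window open, so the effect on the 7.5 count is small. The documents do not support making this part of the point.

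**Conclusion.** The concern holds as a minor wording defect. Followed as written, the plan's only numerical suspension rule omits an immune-related event whose first or only grade is 5. The omission is probably unintended. Its expected effect is about 0.4 to 1.4 percentage points on the chance of suspension, assuming 1 to 2% of qualifying events are affected, true rates of 20 to 40%, independent subjects and the listed counts. The case for correcting it is that one such event is enough to change the decision at any boundary, and whether it counts should be settled beforehand. The documents do not show that the rule is broadly ineffective or that deaths would escape oversight.

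**What to change.** In both statements of Section 7.5, replace the Grade 3 or 4 range with Grade 3 or higher, and add that a fatal immune-related event counts as not resolved under the 72-hour clause. This changes only what is counted; it touches no dose or patient-management rule.

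The cost is a few words. The boundaries 4/11, 5/15 and 6/20 and the sample size of 20 are unchanged, because the 20% threshold and the confidence level are unchanged. Suspension becomes very slightly more likely. The change does not remove all judgement: someone must still decide whether a death was immune-related, a term that 7.5 does not define.
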